## 7.5 Concomitant Medications and Procedures

All treatment/procedures received by the subject within 30 days prior to the Baseline visit and throughout the treatment period, including the name of the treatment/procedure, must be recorded in the eCRF with end dates, if applicable. Use of prohibited treatment/procedures must be recorded in the eCRF up to the extent of the prohibited time period indicated above. Furthermore, previous use of facial aesthetic treatment/procedures must be recorded for up to 1 year prior to the Baseline visit.

In the event such prohibited therapies are administered during the study period, the Medical Monitor will be contacted to discuss the details of the event. Subject participation will not automatically be discontinued. At a minimum, the event will be documented by the site staff as a protocol deviation, as instructed by the Medical Monitor. Depending upon the nature of the prohibited therapy and the timing relative to the determination of the primary endpoint, the Medical Monitor may make a decision to discontinue the subject.

The decision to administer a prohibited medication/treatment is done with the safety of the study participant as the primary consideration. If the permissibility of a specific medication/treatment is in question, the Medical Monitor should be contacted before the prohibited medication/treatment is administered.

### 7.5.1 Prohibited Treatment and Procedures

Subjects must not undergo any type of facial or cosmetic procedure below the orbital rim, including but not limited to dental, plastic or reconstructive surgery; non-ablative procedures; botulinum toxin injections; laser resurfacing; dermabrasion; lipo-injection; or chemical peel at any time during this study. Other necessary therapies that will not interfere with the response to treatment may be provided to the subject at the discretion of the TI.

The following medications/procedures have either restrictions for usage, or are prohibited during the course of the study and appropriate washout periods noted below must be respected:

## 8 DATA COLLECTION

### 8.1 Electronic Case Report Form

Treatment and follow-up of subjects will be recorded in a 21 CFR part 11 compliant eCRF. Data will be first recorded into the medical record and study specific source document worksheets prior to entry into the eCRF. The study coordinator will refer to these worksheets in conjunction with the medical record in order to complete data entry into the eCRF.

In order to review and electronically sign the eCRF, the TI and BLE will each have an individual login password that will allow them to view only the data that they have generated. The TI and BLE must ensure that they electronically sign for completed eCRFs on a timely basis.

### 8.2 Subject Diaries and Questionnaires

[REDACTED]

[REDACTED]

[REDACTED]

[REDACTED]

[REDACTED]

### 8.3 Photography

Calibrated photographs will be taken at Visit 1 (pre- and post-injection) and at Visits [REDACTED] according to a standardized protocol incorporating appropriate quality control processes [REDACTED]

[REDACTED]

[REDACTED]

## 9 STUDY EVALUATIONS

### 9.1 Informed Consent

The TI (or designate) will explain the benefits and risks of study participation to each subject. Written informed consent must be obtained prior to any study related procedure.

### 9.2 Visit Procedures

#### 9.2.1 Visit 1 (Screening / Enrolment / Treatment)

*Procedures that can be completed up to 14 days before V1 are indicated by “+”*

- Written informed consent+
- UPT (if female subject of childbearing potential) +
- Inclusion / exclusion criteria+
- Medical history and demographics+
- Concomitant medications/treatments+

- Randomization to study treatment (i.e., left side/right side; 1st/2nd order)
- Photography (pre- and post-injection)
- Injection of study devices
- TI Assessments
- BLE Assessments
- Subject Assessments
- CTR Diary
  - *Train subject on proper use and completion*
  - *Train subject in recognizing potentially rare events of injection into the vascular system (as described in the CTR diary), and to contact their doctor immediately if an event is suspected*
- Adverse Event evaluation

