Study Design	This is a randomized, controlled, single-blinded, within-subject (split-face), multicenter, prospective study to investigate whether RHA®4 injected in NLFs with a cannula ([REDACTED]) is non-inferior to RHA®4 injected in NLFs with a sharp needle ([REDACTED]) for the correction of moderate to severe NLFs as determined by the Blinded Live Evaluator (BLE) using the NLF-WSRS (validated NLF Wrinkle Severity Rating Scale) [REDACTED]. At screening, the Treating Investigator (TI) and Blinded Live Evaluator (BLE) will evaluate subjects' NLF severity to confirm eligibility and to establish a pre-treatment score for assessing aesthetic improvement (i.e., moderate to severe bilateral nasolabial folds; grade 3 or 4 on the five-point NLF-WSRS; symmetrical in terms of grade). BLE and TI must independently agree that the criterion is met; however, strict concordance of severity is not required. [REDACTED] [REDACTED]		

Hypothesis	RHA®4 injected in NLFs with a cannula is non-inferior to RHA®4 injected in the NLFs with a sharp needle for the correction of moderate to severe NLFs as determined by the NLF-WSRS (validated NLF Wrinkle Severity Rating Scale) [REDACTED]. [REDACTED] [REDACTED] [REDACTED]
Objectives	1. Demonstrate the non-inferiority of RHA®4 injected in the NLFs with a cannula versus the control (RHA®4 injected in NLF with a sharp needle) [REDACTED] for the correction of moderate to severe NLFs. Assessment of non-inferiority will be based on the change from Baseline in NLF-WSRS [REDACTED] as rated by the Blinded Live Evaluator (BLE) at each investigative site. 2. Evaluate the safety of RHA®4 injected in NLF with a cannula versus the control [REDACTED]
Inclusion Criteria	1. Outpatient, male or female of any race, 22 years of age or older. 2. Female subjects of childbearing potential must have a negative UPT at Visit 1 and practice a reliable method of contraception throughout the study. [REDACTED] [REDACTED] [REDACTED] [REDACTED] 3. Moderate to severe bilateral nasolabial folds (grade 3 or 4 on the five-point NLF-WSRS). BLE and TI must independently agree that the criterion is met; however, strict concordance of severity not required [REDACTED]

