### 7.2 Injection of Study Devices

At Visit 1, each randomized subject will receive injections of RHA®4 injected with cannula into the NLF of the left or right side of the face, and injections of the control device (i.e. RHA®4 injected with a sharp needle) into the contralateral NLF.

[REDACTED]

[REDACTED]

[REDACTED]

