### 7.4.1 Other Study Supplies

Supplies that are unique to the study will be provided by [REDACTED] (e.g., UPTs, photographic equipment, source document worksheets, etc.). The site is responsible for routine supplies related to pre-/post-injection care (e.g., alcohol wipes, gauze, etc.).

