#### **9.4.5 Pregnancy and Contraception**

All women of childbearing potential who participate in the study should be counseled on the need to practice adequate birth control and on the importance of avoiding pregnancy during study participation by using effective birth control methods (e.g., oral contraceptive, condom, IUD, injectable contraceptive, diaphragm or vasectomized partner). Male subjects have no contraceptive restrictions. Women should be instructed to contact the TI or study staff immediately if pregnancy occurs or is suspected.

Pregnancy testing will be conducted prior to administration of the study device on every woman of childbearing potential. A woman who is found to be pregnant at Visit 1 will be excluded from the study and considered to be a screen failure.

A woman who becomes pregnant during the study after the first injection will not receive further injections and will be followed for safety purposes. The assessments scheduled for the Exit visit are required to be performed as soon as possible after learning of the pregnancy.

Pregnancies will be recorded using the Pregnancy Form and will not be considered as an AE.

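### Inclusion criterion 2 ties the negative pregnancy test to Visit 1, the injection visit, but the Visit 1 schedule allows the test up to 14 days earlier

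*Protocol*

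**What the plan says.** Synopsis, inclusion criterion 2: "Female subjects of childbearing potential must have a negative UPT at Visit 1". The criterion also requires reliable contraception during the study, and redacted text follows it.

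Section 7.2 fixes the day of treatment: "At Visit 1, each randomized subject will receive injections of" the filler, by cannula on one side and by needle on the other.

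Section 9.2.1 lists the Visit 1 procedures under a note that reads "Procedures that can be completed up to 14 days before V1 are indicated by" a plus sign. The UPT line carries the plus sign: "UPT (if female subject of childbearing potential". So does the line "Inclusion / exclusion criteria". The visible lines for randomization, photography and injection do not.

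Section 9.4.5 has two relevant sentences. One concerns the test: "Pregnancy testing will be conducted prior to administration of the study device on every woman of childbearing potential". The other gives the consequence of a positive finding: "A woman who is found to be pregnant at Visit 1 will be excluded from the study and considered to be a screen failure".

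**The concern.** Criterion 2 names the visit at which the negative result must be obtained. The schedule lets the same test, and the eligibility check that depends on it, be finished before that visit. Sites work from the visit schedule, so a coordinator could test early, sign off eligibility, and treat at Visit 1 without testing again. A monitor applying criterion 2 could then record an eligibility deviation for a subject whom the site believed it had handled correctly.

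Two things are at stake. A pregnancy that becomes detectable between an early test and the injection could be missed. And with 3 to 4 sites, the same criterion could be applied in two ways.

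**Working it through.** The plan states no figure to reproduce. The check is a comparison of texts and the test-to-injection interval that each one permits.

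1. **Day of injection.** Section 7.2 places it at Visit 1. Take this as day 0.
2. **Criterion 2 (synopsis).** The negative UPT must be at Visit 1. Longest interval: 0 days.
3. **Section 9.2.1.** The UPT line is marked, and a marked procedure may be done up to 14 days before V1. Longest interval if the test is not repeated: 14 days.
4. **Section 9.4.5, testing sentence.** The test must come before the device is administered, with no maximum interval. A test on day 0 and a test 14 days earlier both comply, so the sentence does not settle the matter.
5. **Section 9.4.5, screen-failure sentence.** It says what happens to a woman found pregnant at Visit 1. It does not schedule a test, so it is not counted on either side.

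The conflict is therefore between one criterion and one mark in the schedule. Without a same-day repeat the two rules differ by 14 − 0 = 14 days. If a same-day repeat is required in text that cannot be read, they differ by 0 − 0 = 0 days.

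Places where such a requirement could sit are the redacted text after criterion 2 in the synopsis, criterion 2 in Section 5.1 (not readable), the part of the Section 9.2.1 list between the concomitant-medication line and the randomization line, and the study schematic (Figure 1, not shown).

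The number of subjects affected cannot be derived. The documents do not say how many women of childbearing potential would be enrolled, or how many would be tested early.

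**The case against.** The best defence is that the texts can be reconciled. Section 9.2.1 is headed as a screening, enrolment and treatment visit, so a test at Visit 1 might mean the test scheduled under that heading, with its window. The wording of the note defeats this: it describes procedures done before V1, which sets the window apart from the visit.

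A second defence is that the window is permissive while the criterion is mandatory, and that testing on the day satisfies both. That is correct, and it shows that a careful site can comply. It does not stop another site from relying on the schedule, because the eligibility check carries the same mark.

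The third defence carries the most weight: the harm depends on text that cannot be read. A reader might infer that the protocol has no same-day repeat test. The documents do not support that, because the natural places for one are hidden. A reader might also take the screen-failure sentence in Section 9.4.5 as a second rule requiring a test at Visit 1. It is not one; it fits either timing.

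Finally, required contraception, counselling, the rule that a woman who becomes pregnant after the first injection receives no more, and pregnancy follow-up all limit the consequences. This stands, and it keeps the point minor.

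**Conclusion.** The inconsistency is real on the readable text: a woman tested early under Section 9.2.1 and not retested would not meet criterion 2 as written, and could be injected on a result up to 14 days old. That safety consequence assumes that no redacted or unreadable passage requires a repeat on the day; if one does, the interval is 0 days and only a cross-reference is lacking.

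The point is minor. It concerns subject protection and uniform application of one eligibility criterion, and it has no effect on the primary non-inferiority analysis. It would be too strong to describe it as a demonstrated gap in pregnancy screening.

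**What to change.** Either of two edits to Section 9.2.1 is enough:

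- Remove the plus sign from the UPT line, so that the test is done at Visit 1 before randomization and injection.
- Keep the plus sign for an early screening test, and add a line requiring a repeat UPT on the day of injection, before randomization, for any woman tested before Visit 1.

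The remaining eligibility items can stay in the early window, with criterion 2 confirmed at Visit 1. Section 9.4.5 needs no change, since its testing sentence agrees with either edit. If hidden text already requires a same-day repeat, a cross-reference to it in Section 9.2.1 suffices.

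Rewording criterion 2 to accept a test within 14 days before V1 would also make the texts agree, but it would leave the longer interval in place. The edits above are preferable because they close it at little cost.

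That cost is one small wording change at the next amendment. Section 7.4.1 already lists the tests among the supplies provided to sites ("UPTs, photographic equipment, source document worksheets"). The first option brings an occasional screen failure on the day of treatment; the second brings one extra urine test for each woman tested early.

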#### 9.2.2 Visit 1a Phone Follow-up (3 days post initial injection ± 1 day)

- CTR diary review
- Concomitant medications/treatments review
- AE review

#### 9.2.3 Visit 2 (██████████)

- Concomitant medications/treatments
- Adverse Event evaluation (including CTR Diary review)

- Photography (if T/U, taken pre-treatment)

- TI Assessments

- Subject Assessments

- Touch-up Injections (TI discretion)

#### 9.2.4 Visit 2a Phone Follow-up Phone (3 Days post-T/U injection $\pm$ 1 day)

- [REDACTED]
- [REDACTED]
- [REDACTED]

#### 9.2.5 Visit 2b ([REDACTED])

##### Visit only for subjects receiving T/U at V2

- Concomitant medications/treatments
- Adverse Event evaluation (including CTR Diary review)
- Photography

- TI Assessments

[figure not shown]

### 9.3 Efficacy

#### 9.3.1 Aesthetic Effectiveness Evaluations

##### 9.3.1.1 Nasolabial Fold Wrinkle Severity Rating Scale

The NLF-WSRS will be assessed at rest by the TI and BLE using the validated 5-grade WSRS photo-numeric scale [REDACTED]

## 9.4 Safety

Safety will be evaluated through a 4-week patient Common Treatment Response (CTR) diary that captures post-injection signs/symptoms, measures of injection site pain and AE reporting based on phone follow-ups and clinic visits.

### 9.4.1 Patient Common Treatment Response Diary

The study coordinator will provide subjects with instructions for daily recording of his/her observations of the CTRs of the study treatments into an electronic diary for the first 4 weeks after each treatment. The diary will be activated after treatment and will be discussed during the 3-day post-injection telephone follow-up. Subjects should complete the diary at approximately the same time each day (i.e., AM or PM).

The subject diary will capture the following CTRs that typically occur following the injection of a dermal filler; specifically, redness, pain, tenderness, firmness, swelling, lumps/bumps, bruising, itching, discoloration, and “other”. The CTR diary will include a detailed glossary describing all signs/symptoms listed in the diary. Subjects will record the presence and the severity of each observed sign/symptom as: none, mild, moderate, or severe.

### 9.4.2 3-Day Telephone Follow-up

The subject will be contacted by telephone by the investigational site approximately 3 days following study injections and will be queried regarding health status and AEs. Information gathered will be documented in the progress notes and upon confirmation at the next clinic visit, data will be entered into the eCRF. The investigational site must attempt at least twice to contact the subject. All failed attempts will also be documented in the study notes.

#### **9.4.5 Pregnancy and Contraception**

All women of childbearing potential who participate in the study should be counseled on the need to practice adequate birth control and on the importance of avoiding pregnancy during study participation by using effective birth control methods (e.g., oral contraceptive, condom, IUD, injectable contraceptive, diaphragm or vasectomized partner). Male subjects have no contraceptive restrictions. Women should be instructed to contact the TI or study staff immediately if pregnancy occurs or is suspected.

Pregnancy testing will be conducted prior to administration of the study device on every woman of childbearing potential. A woman who is found to be pregnant at Visit 1 will be excluded from the study and considered to be a screen failure.

A woman who becomes pregnant during the study after the first injection will not receive further injections and will be followed for safety purposes. The assessments scheduled for the Exit visit are required to be performed as soon as possible after learning of the pregnancy.

Pregnancies will be recorded using the Pregnancy Form and will not be considered as an AE.

#### **9.4.6 Adverse Events**

All observed or volunteered AEs regardless of treatment group or suspected causal relationship to the study device(s) will be recorded in the eCRF. Subjects will be questioned for the occurrence of any new or worsening signs or symptoms at each visit by the following methods:

- Information volunteered by the subject
- Open ended and non-leading questions such as: Have you had any health problems since your last visit?
- Observation by the investigational team, other care providers or relatives

##### **9.4.6.1 Definition of an Adverse Event**

An AE is any untoward medical occurrence in a subject administered the study device and which may, but does not necessarily, have a causal relationship with the device. An AE can therefore be any unfavorable or unintended sign (for example an abnormal laboratory finding), symptom or disease temporally associated with the use the study device, whether or not considered related to that device.

AEs may include, but are not limited to, subjective or objective symptoms spontaneously offered by the subject, solicited via the diary and subject interviews, uncovered by review of concomitant medications or therapies, and/or observed by the study site staff. The TI will determine the description (sign, symptom, or diagnosis), onset, resolution, seriousness, severity, cause and action taken for any event.

A series of horizontal black bars of varying lengths, likely representing data in a bar chart. The bars are arranged vertically and are set against a white background. The lengths of the bars decrease from top to bottom. The first bar is the longest, followed by a shorter bar, then a very long bar, then a medium bar, then a short bar, then a very long bar, then a medium bar, then a short bar, then a very long bar, then a medium bar, then a short bar, and finally a very long bar at the bottom.

#### **9.4.9 Serious Adverse Events (SAEs) and Unexpected Adverse Device Effects (UADEs)**

A SAE is defined as any unfavorable medical occurrence that meets any of the following:

1. Results in death.
2. Is life-threatening: “Life-threatening” refers to an event in which the subject was at risk of death at the time of the event; it does not refer to an event, which hypothetically might have caused death if it were more severe.
3. Requires inpatient hospitalization or prolongation of existing hospitalization: Planned and routine hospital admissions for pre-existing conditions are not considered SAEs and do not require reporting as an AE unless the condition has worsened beyond what would reasonably be expected for that subject. If a subject experiences an additional AE that prolongs a pre-planned hospitalization this is considered to be an SAE and should be reported as an SAE. Pre-planned admissions must be recorded in the subject’s source documentation.
4. Results in persistent or significant disability/incapacity.
5. Is a congenital anomaly or birth defect resulting from a pregnancy that occurred during the study.

6. Is an important medical event: Important medical events that may not be immediately life-threatening or result in death or hospitalization but may jeopardize the subject or may require intervention to prevent one of the other outcomes listed above should usually be considered serious.

A **UADE** is defined as any device-related AE that meets any of the following:

1. Is not identified in nature, severity or frequency in current literature on the product.
2. Is life threatening, even if temporary in nature.
3. Results in permanent impairment of a body function or permanent damage to a body structure.
4. Necessitates medical or surgical intervention to preclude permanent impairment of a body function or permanent damage to a body structure.
5. Any device malfunction that would be likely to cause or contribute to a death or serious injury if the malfunction were to recur.

#### **9.4.10 Causality Assessment**

The TI's assessment of an AE's relationship to the study device is part of the documentation process, but it is not a factor in determining what is or is not reported in the study. If there is any doubt as to whether a clinical observation is an AE, the event will be reported. The TI will assign the causality assessment according to his/her clinical experience and the subject's description of the event. The Sponsor will be responsible for the final causality judgment. The causal relationship should be classified according to the following criteria (not all variables need to be present to be indicative of relationship to the device):

***Definitely related:***

- The temporal sequence of AE onset relative to injection of study device is reasonable.
- The AE is more likely explained by the study device or procedure than by another cause.
- The AE shows a pattern consistent with previous knowledge of the study device.

***Probably related:***

- The temporal sequence of AE onset relative to injection of study device is reasonable.
- The AE is more likely explained by the study device or procedure than by another cause.

***Possibly related:***

- The temporal sequence of AE onset relative to injection of study device is reasonable.
- The AE could have been due to another equally likely cause.

